10.2.1. Investigator's Global Assessment (IGA)

The IGA is a 5-point scale used by the Investigator or trained designee to evaluate the global severity of PN and the clinical response to a treatment (see [Table 10-1](#)).

Table 10-1: Investigator Global Assessment Scale

0	Clear	No nodules
1	Almost Clear	Rare palpable pruriginous nodules
2	Mild	Few palpable pruriginous nodules
3	Moderate	Many palpable pruriginous nodules
4	Severe	Abundant palpable pruriginous nodules

IGA treatment success is defined as 0 (clear) or 1 (almost clear) on the IGA scale.

IGA will be collected at Baseline/Day 1, Week 4, Week 8, Week 12, Week 16, Week 20, Week 24 and Early Termination or any unscheduled visit. In case of missing assessment at Baseline, the last available assessment prior study drug administration will be considered as Baseline.

IGA will be summarized as a categorical and continuous variable at each analysis visit. Absolute change from Baseline for the IGA score will also be presented in the summary on the ITT and Per-Protocol Population.

The proportion of subjects maintaining IGA success and subjects with increase in IGA ≥ 2 points from baseline will be summarized on the ITT based on OC. The estimate of treatment unadjusted and strata-adjusted differences with the corresponding two-sided 95% confidence intervals, and p-values from the CMH test will be presented.

The analysis will be repeated:

- on Per-Protocol Population, based on OC
- on ITT population, imputing missing values with non-responder imputation

Line plot for proportion of subjects maintaining IGA success and proportion of subjects with increase in IGA ≥ 2 points from baseline, both using non-responder imputation, will be for the ITT Population.

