### 9.6.2     Rescue Therapy

Rescue therapies are not permitted in this study. Subjects enrolled in this study have demonstrated a clinical response to nemolizumab; therefore, if a subject experiences relapse, they will be discontinued from this study and may be eligible to continue to receive nemolizumab by re-enrolling in the LTE study (see [Figure 2](#)).

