If a subject meets the criteria for relapse at any point, the subject will exit the study and re-enter the LTE study (see [Figure 4-1](#)). Subjects who exit the study before Week 24 should complete an early termination (ET) visit. Subjects who complete the study through Week 24 are eligible to re-enroll in the LTE study.

Subjects who prematurely discontinue study drug for reasons other than relapse will be encouraged to complete the scheduled study visits. These subjects will only be eligible for re-enrollment in the LTE study if they continue with study visits through Week 24.

Subjects who discontinue the study for reasons other than relapse before Week 24 or who will not continue nemolizumab treatment in the LTE study should complete a follow-up visit, 12 weeks (± 7 days) after the last study drug injection.

[figure not shown]
Follow-up Period

This document is confidential.

A follow-up visit will be conducted 8 weeks (± 7 days) after completing the treatment period and/or 12 weeks (± 7 days) after the last study drug injection for all subjects who will not continue nemolizumab treatment in the LTE study. Twelve weeks corresponds to approximately 5 half-lives of nemolizumab when administered subcutaneously Q4W at the doses used in this study.

An overview of the study is presented in [Figure 4-2](#).

Figure 4-2: Study Design

*Clinical responder is defined as a subject with an Investigator Global Assessment (IGA) score= 0 or 1 and improvement in Peak Pruritus Numeric Rating Scale (PP NRS) score of ≥ 4 points from baseline of the lead-in study at Week 52 visit of the LTE study. Note: Lead-in study baseline is defined as baseline PP NRS score in the Phase 3 studies RD.06.SPR.202685 or RD.06.SPR.203065 for subjects who rolled over into the LTE from these studies. For subjects who entered the LTE study from the Phase 2 study RD.03.SPR.115828, the baseline PP NRS score at entry into the LTE study RD.06.SPR.202699 will be used.

** Relapse is defined as an increase in weekly average of PP NRS score ≥ 4 points from baseline or an

This document is confidential.

increase in IGA score ≥ 2 from baseline at any point during the study. Subjects who relapse at any point during the treatment period or who complete through Week 24 are eligible for LTE re-entry.

Abbreviations: BL = baseline; LTE = long-term extension; R = randomization; W = week.

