10.2. Secondary Efficacy Endpoints

The following secondary endpoints are to be analysed at the scheduled visits:

Endpoint	Analysis Visit	Analysis to be done on which Population	Statistical Tests
Proportion of subjects maintaining IGA success at each scheduled visit	Baseline, Week 4, Week 8, Week 12, Week 16, Week 20, Week 24	On the ITT and Per-Protocol Population	CMH
Proportion of subjects with increase in IGA ≥ 2 points from baseline at each scheduled visit	Baseline, Week 4, Week 8, Week 12, Week 16	On the ITT and Per-Protocol Population	CMH
Proportion of subjects with increase in PP NRS score ≥ 4 points from baseline at each scheduled visit	Baseline, Week 4, Week 8, Week 12, Week 16, Week 20, Week 24	On the ITT and Per-Protocol Population	CMH
Absolute and percent change from baseline in PP NRS at each scheduled visit	Baseline, Week 4, Week 8, Week 12, Week 16, Week 20, Week 24	On the ITT and Per-Protocol Population	ANCOVA
Absolute and percent change from baseline in PP NRS at each scheduled visit	Baseline, Week 4, Week 8, Week 12, Week 16, Week 20, Week 24	On the ITT	MMRM

This document is confidential.

Endpoint	Analysis Visit	Analysis to be done on which Population	Statistical Tests
Absolute and percent change from baseline in SD NRS at each scheduled visit	Baseline, Week 4, Week 8, Week 12, Week 16, Week 20, Week 24	On the ITT and Per-Protocol Population	ANCOVA
Absolute and percent change from baseline in SD NRS at each scheduled visit	Baseline, Week 4, Week 8, Week 12, Week 16, Week 20, Week 24	On the ITT	MMRM
Change from baseline in DLQI at each visit	Baseline, Week 16, Week 24	On the ITT Population	ANCOVA

Abbreviations: CMH=Cochran-Mantel-Haenszel; DLQI=Dermatology Life Quality Index; IGA=Investigator Global Assessment; PP=Peak Pruritus; SD=Sleep Disturbance.

Binary secondary efficacy endpoints will be analyzed using a Cochran-Mantel-Haenszel test adjusted for dosing regimen based on OC and imputation with missing efficacy response considered as the non-responder (i.e., IGA success) and missing relapse response considered as a relapse (i.e., increase in PP NRS or IGA). The estimate of treatment unadjusted and strata-adjusted differences with the corresponding two-sided 95% confidence intervals, and p-values from the CMH test will be presented.

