The proportion of subjects with PP NRS with ≥ 4 in increase from baseline will be summarized on the ITT based on OC. The estimate of treatment unadjusted and strata-adjusted proportion differences with the corresponding two-sided, 95% CI, and p-values from the CMH test will be presented.

The analysis will be repeated:

This document is confidential.

- on Per-Protocol Population, based on OC
- on ITT population, imputing missing values with non-responder imputation

Line plot for proportion of subjects with PP NRS ≥ 4 increase will be presented on the ITT Population using non-responder imputation.

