	14.1.4.4	Summary of Prohibited Medications during Treatment Period by ATC level and Preferred Term	ITT Population
	14.1.4.5	Summary of Prohibited Medications during Follow-up Period by ATC level and Preferred Term	ITT Population
14.1.5		Treatment Compliance	

This document is confidential.

Header	Table Number	Name	Analysis Set
	14.1.5.1	Summary of Exposure to Study Drug	Safety Population
14.2		Efficacy Data	
14.2.1		Primary Efficacy Parameters	
	14.2.1.1.1	Time to Relapse	ITT Population
	14.2.1.1.3	Sensitivity Analysis of Time to Relapse	Per-Protocol Population
	14.2.1.1.5	Sensitivity Analysis of Time to Relapse - using Actual Stratifications	ITT Population
	14.2.1.1.7	Sensitivity Analysis of Time to Relapse - Removing COVID-19 affected Visits	ITT Population
14.2.2		Secondary Efficacy Parameters	
14.2.2.1		Secondary Efficacy Parameter: IGA	
	14.2.2.1.1	Summary of IGA - OC	ITT Population
	14.2.2.1.2	Summary of IGA - OC	Per-Protocol Population
	14.2.2.1.3	Summary of Proportion of Subjects with maintaining IGA Success - OC	ITT Population
	14.2.2.1.4	Analysis of Proportion of Subjects with maintaining IGA Success - OC	ITT Population
	14.2.2.1.5	Analysis of Proportion of Subjects with maintaining IGA Success - OC	Per-Protocol Population
	14.2.2.1.6	Analysis of Proportion of Subjects with maintaining IGA Success - Missing as non-responder	ITT Population
	14.2.2.1.8	Summary of Proportion of Subjects with increase in IGA \geq 2 points from baseline - OC	ITT Population
	14.2.2.1.9	Analysis of Proportion of Subjects with increase in IGA \geq 2 points from baseline - OC	ITT Population
	14.2.2.1.10	Analysis of Proportion of Subjects with increase in IGA \geq 2 points from baseline - OC	Per-Protocol Population

This document is confidential.

Header	Table Number	Name	Analysis Set
	14.2.2.1.11	Analysis of Proportion of Subjects with increase in IGA \geq 2 points from baseline - Missing as non-responder	ITT Population
14.2.2.2		Secondary Efficacy Parameter: Peak Pruritus Numeric Rating Scale	
	14.2.2.2.1	Summary of Weekly PP NRS – OC	ITT Population
	14.2.2.2.2	Summary of Weekly PP NRS – OC	Per-Protocol Population
	14.2.2.2.3	Summary of Proportion of Subjects with Weekly PP NRS increase \geq 4	ITT Population
	14.2.2.2.4	Analysis of Proportion of subjects with increase in PP NRS score \geq 4 points from baseline - OC	ITT Population
	14.2.2.2.5	Analysis of Proportion of subjects with increase in PP NRS score \geq 4 points from baseline – OC	Per-Protocol Population

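### The observed-case by-visit relapse and IGA-success results leave out subjects who have already relapsed, and the imputed version is mislabelled for the two worsening endpoints

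*SAP*

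**What the plan says.** **Exit at relapse.** SAP 4.1: "If a subject meets the criteria for relapse at any point, the subject will exit the study and re-enter the LTE study". Protocol 9.6.2 agrees that on relapse "they will be discontinued from this study and may be eligible to continue to receive nemolizumab by re-enrolling in the LTE study". An early-termination (ET) visit is done, and SAP 8.4 places ET data in an analysis window by study day. The relapse can therefore count at that window only.

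**OC analysis.** Protocol 14.3 says that OC involves no imputation. In SAP 10.2.1, IGA success and IGA rise of at least 2 "points from baseline will be summarized on the ITT based on OC". In SAP 10.2.2, the PP NRS rise of at least 4 "in increase from baseline will be summarized on the ITT based on OC". Each has CMH differences, confidence intervals and p-values. The per-protocol repeat in both sections is also OC, and the SAP 17 index lists no imputed per-protocol table for these endpoints (14.2.2.1.5, 14.2.2.1.10 and 14.2.2.2.5 are all OC).

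**Imputed analysis.** SAP 10.2 gives the direction by endpoint. Missing IGA success is a non-responder, and for the two increase endpoints "missing relapse response considered as a relapse". Protocol 14.3.2 has the same rule, and SAP 8.3 imputes missing binary data to failure. SAP 10.2.1 and 10.2.2, however, describe the repeat as "on ITT population, imputing missing values with non-responder imputation". The title of Table 14.2.2.1.11, on the IGA rise, ends "points from baseline - Missing as non-responder". Table 14.2.2.2.6 and the line plots for the two increase endpoints (SAP 18) use the same label.

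**The concern.** The missing data are caused by the outcome. A subject who relapses at Week 8 is in neither the numerator nor the denominator of the OC proportion at Week 24. Protocol 7.2 says the efficacy endpoints are designed to measure maintenance or loss of response. The late-visit OC proportions instead approximate new relapse among those still on study. The arm that relapses more loses more of its failures, so the contrast shrinks as the trial goes on. OC by-visit results could then look much weaker than the time-to-relapse result from the same subjects.

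The label is a second, smaller problem. For IGA success, the event is good and *non-responder* is the right word for a missing value. For a rise in IGA or PP NRS, the event is bad. If the response variable is coded 1 for an increase and missing is set to non-response, a subject who has already relapsed becomes a non-event. The CMH example code in SAP 20.1 uses a generic response variable and does not settle the coding.

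**Working it through.** The plan states no relapse rate, effect size or power for these endpoints, so there is no figure to reproduce. Both checks below rest on assumed rates. I use 20 per arm: SAP 4.3 and protocol 14.1 expect about 40 subjects at 1:1. SAP 4.1 says about 100, but the proportions in check 1 do not depend on this.

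**Check 1: constant hazard.** Assumptions: six post-baseline visits (Weeks 4 to 24), one absorbing relapse event, each relapse scored at the visit closing its interval, and no other dropout. With p the 24-week relapse probability, survival per visit interval is s = (1 − p)^(1/6). At Week 24:

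- cumulative relapse, which here equals missing counted as relapse: p
- OC proportion: 1 − s
- missing read literally as no increase: s^5 × (1 − s)
- expected number observed per arm: 20 × s^5

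Nemolizumab, p = 0.10: s = 0.9826, OC 1.7%, literal reading 1.6%.

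Placebo, p = 0.50: s = 0.8909, OC 10.9%, literal reading 0.561 × 0.109 = 6.1%, observed 20 × 0.561 = 11.2.

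| Placebo vs nemolizumab relapse | Cumulative difference | OC difference | Literal no-increase difference |
|---|---|---|---|
| 30% vs 10% | 20 points | 4 | 2.7 |
| 50% vs 10% | 40 points | 9 (10.9% vs 1.7%) | 4.5 (6.1% vs 1.6%) |
| 70% vs 10% | 60 points | 16 | 5 |

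The SAP 10.2 table lists the IGA rise only to Week 16, although the endpoint in SAP 5.2 is for each scheduled visit. At Week 16 (fourth visit), cumulative relapse is 1 − s^4. In the 50% vs 10% case that is 37.0% vs 6.8%, a difference of 30 points, while OC still shows 10.9% vs 1.7%. The effect does not depend on Week 24.

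**Check 2: direct counts at Week 24 with some other dropout.** Assumed counts per arm are earlier relapses / new relapses at Week 24 / non-relapse dropouts. Results are nemolizumab vs placebo.

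| Scenario | Nemolizumab; placebo | Cumulative relapse | OC | Missing as relapse |
|---|---|---|---|---|
| Low | 1/0/1; 5/1/1 | 5% vs 30% | 0/18 vs 1/14 | 2/20 vs 7/20 |
| Middle | 2/1/1; 10/2/1 | 15% vs 60% | 1/17 vs 2/9 | 4/20 vs 13/20 |
| High | 3/1/2; 14/1/2 | 20% vs 75% | 1/15 vs 1/4 | 6/20 vs 17/20 |

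Cumulative differences of 25, 45 and 55 points become 7, 16 and 18 points on OC. In the middle case the unstratified Fisher p-value is 0.27 on OC and 0.01 with missing as relapse (for orientation only). Missing as relapse recovers the cumulative differences exactly here only because dropout was set equal between arms.

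**IGA success.** The distortion is smaller. Every IGA relapse (0 to 2 or more, 1 to 3 or more) loses success, but a move from 1 to 2 loses success without meeting the IGA relapse criterion. Such a subject can stay, and OC still counts the loss.

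**The case against.** The strongest reply is that the plan already contains the right analysis. SAP 10.2, SAP 8.3 and protocol 14.3.2 all count a missing relapse response as a relapse or failure, and the imputed ITT tables are in the index. A reader might infer from the label that both the OC and the imputed analyses lose relapsed subjects. The documents do not support that. Under the stated rule these subjects stay in the ITT denominator as failures. No text says that missing means no worsening, and SAP 14 lists no departure from the protocol rule. That coding would arise only if someone followed the label against SAP 10.2, and even then subjects would be miscoded rather than dropped. For IGA success the label is correct, and its line plot counts relapsed subjects as failures. All of this stands.

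It can also be said that OC leads only by order of mention: SAP 10.2 and protocol 14.3.2 name OC and imputation together, and the protocol synopsis says one or the other. That is fair, but it means nothing ranks the imputed version first, and the per-protocol outputs have no imputed version at all.

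The illustration applies one relapse rate, in effect that of the composite, to endpoints that are its components. That also stands: the figures show the mechanism and its rough scale, and they do not forecast any one endpoint.

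**Conclusion.** The concern holds in limited form. The OC by-visit proportions condition on not having already exited for relapse. They understate cumulative loss of response and the treatment difference at later visits, clearly for the two increase endpoints and less so for IGA success. Under the assumed 50% vs 10% relapse, 40 points shrink to about 9. Over the other assumed cases, differences of 20 to 60 points shrink to roughly 4 to 18. These sizes rest wholly on assumed rates, because the documents give none.

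The imputed ITT analysis is correctly defined. Its label conflicts with SAP 10.2 for the two increase endpoints, which is an ambiguity with a specific programming risk and not a wrong analysis. The primary Cox and Kaplan-Meier analysis of time to relapse is unaffected. This is therefore a correction to secondary results, best made before unblinding.

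**What to change.** 1. In SAP 10.2, 10.2.1 and 10.2.2, name the imputed analysis as the main by-visit analysis: an observed relapse is carried forward, and other missing values count as relapse or as not maintaining IGA success. On ITT this gives the same coding after exit as the existing SAP 10.2 rule; the change is its rank and an explicit statement. Add the same analysis for the per-protocol set.
2. Keep OC as supportive, with titles that say it describes subjects still on study.
3. For the two increase endpoints, replace *non-responder* with *missing counted as relapse* in the text, table titles and line plots. Leave it for IGA success.

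The cost is SAP wording, one derivation and a few extra per-protocol tables, with no new data. The drawback is that subjects who drop out for other reasons, or who relapse on the other criterion, count as relapsed on a component they may not have met. A footnote giving the number in each group would make that visible.

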10.2.2. Pruritus Numeric Rating Scale (NRS)

The Pruritus NRS is a scale to be used by the subjects to report the intensity of their pruritus (itch) during the last 24 hours. Peak pruritus (PP NRS) is an assessment of the maximum itch intensity in that period.

This document is confidential.

Subjects will be asked the following question:

- CCI

The Baseline PP NRS will be the score of Week 52 visit from LTE trial.

PP NRS at all follow-up visits will be determined as an average of 7 consecutive days data up to the target study day and will be set to missing if less than 4 days data are available. Subjects will receive instructions on how to record their PP NRS scores and will complete the assessment once daily in the evening throughout the clinical study (including the run-in and the follow-up period).

PP NRS will be determined by an average as described above at every week from Baseline to Week 24 as a continuous variable.

Descriptive summary of PP NRS (OC) will be provided on the ITT and Per-Protocol Populations. Absolute change and percent change from Baseline for the PP NRS will also be included in the summary on the ITT and Per-Protocol Populations.

Absolute change from Baseline in PP NRS will be analyzed using ANCOVA based on OC, including treatment group dose regimen as factors with baseline value as covariate. The least squares means (LSMeans), standard error of LSMeans, and 95% CI for change from baseline, as well as the difference in LSMeans between the treatment groups, the two-sided 95% CI, and associated p-value will be presented. Percentage change from Baseline in PP NRS will not be analyzed because of the small sample size and potential high skewness of the data.

The analysis will be repeated:

- on Per-Protocol Population, based on OC

on ITT population, based on OC and using MMRM approach, including treatment group and dose regimen as factor, visit, interaction term between treatment and visit, and baseline value as covariate. Kenward-Roger approximation is used to estimate denominator degrees of freedom. An unstructured covariance is used to model the within-patient errors in the analysis. While applying the model, if convergence criteria not met with unstructured covariance matrix, then below mentioned covariance matrix will be applied to achieve convergence of the model. The matrix with the minimum AIC criteria will be selected for the further analysis.

- Compound Symmetry (CS)
- Ar(1) – Autoregressive (1)

The proportion of subjects with PP NRS with ≥ 4 in increase from baseline will be summarized on the ITT based on OC. The estimate of treatment unadjusted and strata-adjusted proportion differences with the corresponding two-sided, 95% CI, and p-values from the CMH test will be presented.

The analysis will be repeated:

This document is confidential.

- on Per-Protocol Population, based on OC
- on ITT population, imputing missing values with non-responder imputation

Line plot for proportion of subjects with PP NRS ≥ 4 increase will be presented on the ITT Population using non-responder imputation.

10.2.3. Sleep Disturbance Numeric Rating Scale (SD NRS)

The SD NRS is a scale to be used by the subjects to report the degree of their sleep loss related to PN.

The baseline SD NRS will be the score of Week 52 visit from LTE trial.

Subjects will be asked the following question:

- CCI

Descriptive summary of SD NRS (OC) will be provided on the ITT and Per-Protocol Population. Absolute change and percent change from Baseline will also be included in the summary.

Absolute change from Baseline in SD NRS will be analyzed using ANCOVA based on OC, including treatment group dose regimen as factors with baseline value as covariate. The least squares means (LSMeans), standard error of LSMeans, and 95% CI for change from baseline, as well as the difference in LSMeans between the treatment groups, the two-sided 95% CI, and associated p-value will be presented. Percentage change from Baseline in SD NRS will not be analyzed because of the small sample size and potential high skewness of the data.

The analysis will be repeated:

- on Per-Protocol Population, based on OC

on ITT population, based on OC and using MMRM approach, including treatment group and dose regimen as factor, visit, interaction term between treatment and visit, and baseline value as covariate. Kenward-Roger approximation is used to estimate denominator degrees of freedom. An unstructured covariance is used to model the within-patient errors in the analysis. While applying the model, if convergence criteria not met with unstructured covariance matrix, then below mentioned covariance matrix will be applied to achieve convergence of the model. The matrix with the minimum AIC criteria will be selected for the further analysis.

- Compound Symmetry (CS)
 - Ar(1) – Autoregressive (1)
-

This document is confidential.

10.2.4. Dermatology Life Quality Index

The DLQI is a validated 10-item questionnaire covering domains including symptoms/feelings, daily activities, leisure, work/school, personal relationships, and treatment.

The subject will rate each question ranging from 0 (not at all) to 3 (very much). The DLQI total score is calculated by summing each questionnaire. Total score will have a maximum score of 30 and a minimum of 0. The higher score indicated a poorer quality of life.

DLQI will be collected at Baseline, Week 16, Week 24 and Early Termination. DLQI total score will be summarized as a continuous variable using OC on the ITT Population. Absolute change and percentage change from Baseline in DLQI total score will also be summarized.

Absolute change from Baseline in DLQI will be analyzed using ANCOVA based on OC, including treatment group dose regimen as factors with baseline value as covariate. The least squares means (LSMeans), standard error of LSMeans, and 95% CI for change from baseline, as well as the difference in LSMeans between the treatment groups, the two-sided 95% CI, and associated p-value will be presented. Percentage change from Baseline in DLQI will not be analyzed because of the small sample size and potential high skewness of the data.

This document is confidential.

11. Pharmacokinetics

The serum concentration of Nemolizumab will be assessed at Baseline, Week 24 and Early Termination visit. PK analyses are required during any unscheduled visit conducted for safety reasons. As a guideline, PK samples should be collected at approximately the same time of day throughout the study, to the extent possible, before study drug injection (pre-dose samples).

